STATISTICAL ANALYSIS PLAN

Delayed loading following repair of ruptured Achilles tendon
– A randomized controlled trial

Index:

INDEX:	2
BACKGROUND	3
Purpose	3
Hypotheses	3
STUDY DESIGN	3
Participants	4
Blinding	4
Sample size calculation	5
OUTCOME ASSESSMENTS	5
Primary outcome	5
Secondary outcomes	5
POPULATION TO BE ANALYZED	5
Intension-to-treat (ITT)	6
Per protocol (PP)	6
ANALYSIS	6
Primary outcome	7
Secondary outcome	7
Table of the analysis	7
REFERENCES	8

Background

Leisure time physical activity is unquestionably associated with numerous health benefits.

However, some of these recreational activities are also accompanied with some increased risk of injury. For example, there appears to be an increased risk of Achilles tendon ruptures with some recreational sports (1). Specifically, this increased incidence can be seen in high-impact sports, including badminton, volleyball, and soccer (2, 3). Acute Achilles tendon ruptures occurs in both men and women but is most frequent in men 30-50 years of age that participate in recreational sports periodically (1, 4, 5). The prevalence is reported to be ~ 18 per 100,000 per year, and the incidence appear to be on the rise (1, 4-6). Yet, evidenced based knowledge of how to best rehabilitate the injury after repair of the rupture is largely absent in the literature, which likely contributes to the reports of persistent muscle weakness, tendon elongation and incomplete return to pre-injury level (7-18). It has been suggested that preventing tendon elongation during rehabilitation improves the clinical outcome, which is the very aim of this project.

Purpose

The purpose of the present study is to investigate if delayed loading following surgical treated Achilles tendon rupture influence the clinical outcome and muscle and tendon structure after one year.

Hypotheses

We hypothesize that delaying the gradual introduction of loading in the initial 26 weeks may reduce the heel-rise deficit (primary outcome) and thus improve the clinical outcome one year after surgery (primary endpoint).

Study design

This study is a single-blinded prospective randomized controlled superiority trial with 2 parallel arms. (The study will be registered by ClinicalTrials.gov). We will examine if delaying initiation of loading in the initial 26 weeks will influence the tendon healing and elongation compared to current accepted clinical guidelines for rehabilitation ('accelerated rehabilitation') of surgically repaired Achilles tendon ruptures. One arm will include current clinical practice that calls for partial weight bearing from week 3, full weight bearing from week 7, and total bracing time 6

weeks. The other arm will not be allowed partial weight bearing with the use of crutches until week 7 and full weight bearing until week 13, and total bracing time is 12 weeks.

Participants

The patient recruitment will be achieved in-house from the emergency clinic and the orthopedic surgery department at Bispebjerg and Frederiksberg Hospital. Potential participants are either identified by the diagnosing doctor, or by the primary investigator through screening of the orthopedic surgery-lists. Furthermore, features of the SP-journal system will be used to support recruitment. For patients identified by the diagnosing doctor, once the diagnosis of Achilles tendon rupture is established, patients are orally informed about the study and if interested in participating they will receive the written attending information ("Deltagerinformation"). Patients identified through the orthopedic surgery-lists will be approached by the primary investigator in person on the day of surgery and will be given the same oral and written information as those identified by the diagnosing doctor. Patients interested in participating will either contact the primary investigator or will be approached in person on the day of surgery, to be screened for eligibility. The orthopedic surgeons will assess all patients after standard procedures and, if surgical intervention is decided, patients will undergo the standard surgical procedure. After surgery, patients will be randomized to one of the two rehabilitation groups:

A) Early mobilization. This constitutes the currently accepted regime and is therefore considered the control group.

B) Delayed mobilization.

Randomization procedure is performed using a computer-generated block randomization (blocks of 4) procedure.

Blinding

Because this is an "open-label" trial the health professionals delivering the interventions and the participants will not be blinded to treatment allocation. Outcome assessors will be blinded to treatment allocation whenever possible: This is of outmost importance, and participants are requested not to disclose their allocation when outcomes are assessed.

Sample size calculation

Based on heel-rise deficit (primary outcome) relative to the uninjured side ($u_A=76\%$, $u_B=90\%$, $\sigma=16$) a sample of $n=21$ is required to detect a difference with a power of 80% (19). To account for drop-outs a sample of 24 in each arm will be recruited.

Outcome assessments

Primary outcome

The primary outcome is heel-rise height deficit on the injured side relative to the uninjured side at one-year follow-up.

Secondary outcomes

The following outcomes are assessed as secondary outcomes:

- Heel-rise work.
- Achilles Tendon Total Rupture Score (ATRS).
- Gastrocnemius and soleus muscle fascicle length and pennation angle.
- Gastrocnemius and soleus tendon and lower limb muscle cross-sectional area.
- Plantarflexion Isokinetic muscle strength.
- Physical activity level (PAS).
- Tendon length.
- Achilles Tendon Resting Angle (ATRA).

Population to be analyzed

To be included in the study, participants must meet the following in- and exclusion criteria:

Inclusion criteria	Exclusion criteria

 • Diagnosed with a traumatic, complete mid-substance Achilles tendon rupture • No contraindications for MRI • Presented within 14 days from injury • Adult (18 to 60 years) • Understand Danish • Manage transport to/from the hospital on their own 	
 • Other injuries affecting their lower limb functions • Prior Achilles tendon rupture • Re-rupture • Smoking • Systemic diseases influencing tendon healing • Anticoagulation treatment • Inability to follow rehabilitation or complete follow-ups • Immunosuppressive treatment including systemic corticosteroid treatment.

Intension-to-treat (ITT)

All participants who are randomized.

Per protocol (PP)

All participants who adhere to the major criteria in the protocol and completed the whole study period and attended 1 year follow-up. Participants with missing data on any of the variables in the model will be excluded from the specific analysis at the specific timepoint.

Analysis

All outcomes will be reported using descriptive statistics. Normally distributed data by the mean and standard deviation and skewed distributions by the median and interquartile range. Binary and categorical variables will be presented using counts and percentages. SAS and Prism will be used for all statistical analysis. Analyses in addition to the descriptive statistics are described below.

Primary outcome

The primary analysis will be an assessment of the between group difference in heel-rise height deficit on the injured side relative to the uninjured side ($((\text{uninjured}-\text{injured})/\text{uninjured}) \times 100$) at one-year follow-up. Intention-to-treat and per-protocol analysis will be conducted. The criteria for being included in the per-protocol analysis is having attended 1 year follow-up tests. An unpaired students t-test will be used to analyze the primary outcome (heel-rise deficit) at the primary endpoint (one year).

Secondary outcome

A mixed model (group x time) that includes all timepoints will be used to analyze the secondary outcomes and the primary outcome. In addition, a correlation matrix for the changes in secondary and primary outcome will be performed, followed by a multiple regression. ATRA will be compared with MRI and correlated.

Table of the analysis

OUTCOME	TIMEPOINTS	UNPAIRED T-TEST	MIXED MODEL	CORRELATION	MULTIPLE REGRESSION
MRI Tendon length CSA tendon CSA muscle Free fat fraction	4		x	x	x
ULTRASOUND Fascicle length Pennation angle Thickness muscle Doppler tendon Thickness tendon	4		x	x	x
HEELRISE Work Height Repetitions	2		x	x	x
ATRA	2		x	x	x
MUSCLE STRENGTH	1	x		x	x
ATRS	2	x		x	x
PAS	2	x		x	x
LIKERT SCALE	1	x			

References

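### The fixed block size of 4 can make up to about a third of assignments certain to a recruiter who sees all past allocations; undisclosed blocks of 4 or 6 remove most of that certainty at almost no cost, but not the guessing

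*Combined protocol and SAP*

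**What the plan says.** Under Study design, Participants, the SAP gives one block size and no variation in it: "Randomization procedure is performed using a computer-generated block randomization (blocks of 4) procedure". Stratification is not mentioned. The Sample size calculation section adds "To account for drop-outs a sample of 24 in each arm will be recruited", which gives 48 patients, or 12 blocks of 4 on one list.

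On recruitment, the Participants section says: "Patients identified through the orthopedic surgery-lists will be approached by the primary investigator in person on the day of surgery". Interested patients "will either contact the primary investigator or will be approached in person on the day of surgery, to be screened for eligibility". On timing: "After surgery, patients will be randomized to one of the two rehabilitation groups".

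The Blinding section says that "the health professionals delivering the interventions and the participants will not be blinded to treatment allocation". Planned total bracing time is 6 weeks in one arm and 12 in the other, so the arms look different in practice. Among the exclusion criteria in Population to be analyzed, one calls for a forecast by whoever screens: "Inability to follow rehabilitation or complete follow-ups".

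**The concern.** With a single known block size, the end of each block can be worked out from what came before. Someone who screens patients and also knows the earlier allocations could then know the next arm before judging eligibility. The exclusion for expected inability to follow rehabilitation is open to judgement, and the two regimes differ in length and restriction. It could therefore be applied differently according to the expected arm, consciously or not. The planned primary analysis is an unpaired t-test with no stated baseline adjustment, so a difference in who enters each arm would pass into the primary comparison. Blinding the outcome assessors does not guard against this. The documents support no size for such an effect, and none is claimed here.

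**Working it through.** **Plan's own figure.** The documents give no predictability figure. The one related number is the sample size, needed below for the cost of the change. With a difference of 90 − 76 = 14, SD 16, 80% power and two-sided 0.05 (assumed; alpha is not stated): n = 2 × (1.960 + 0.842)² × 16² / 14² = 20.5, so 21 per arm, as the SAP says.

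**Fixed blocks of 4: exact.** Inputs: two arms, 1:1 (inferred from 24 per arm), one list of 48. The six equally likely orders are AABB, BBAA, ABAB, BABA, ABBA and BAAB.

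- *Nobody pending.* The fourth assignment is always certain. The third is also certain when the first two agree (AABB, BBAA). Per block: (2 × 2 + 4 × 1)/6 = 1.333. Share: 1.333/4 = 1/3, or 16 of 48. The total over 12 blocks is 12 + Binomial(12, 1/3): possible range 12 to 24, 5th to 95th percentile 13 to 19.
- *One earlier patient always pending.* Only the fourth can be certain, and only when the first two agree: (1/3)/4 = 1/12, or 4 of 48.
- *Two always pending, or past allocations not visible.* 0.
- *Half the patients screened with one pending.* 48 × (0.5/3 + 0.5/12) = 8 + 2 = 10.
- *Best guess, nobody pending.* By position, the chance of being right is 1/2, 2/3, 2/3 and 1; the mean is 17/24 = 70.8%.

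**Sizes 4 or 6: simulated lists of 48.** The recruiter is assumed to know that sizes are 4 or 6 and equally likely, and to know all non-pending past allocations, but not the order of the sizes. Certain means a probability of exactly 0 or 1 given that knowledge.

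| | Fixed 4 | 4 or 6 |
|---|---|---|
| Certain of 48, nobody pending | 16 | 2.7 (5.6%) |
| Certain, one pending | 4.0 | 1.6 |
| Certain, two pending | 0 | 0.5 |
| Best guess, nobody pending | 70.8% | 69.0% |
| Best guess, one pending | 58.3% | 59.1% |

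**Weaker cut-offs, nobody pending.** The table gives the number of the 48 assignments predictable with at least the stated probability. With fixed blocks of 4 the prediction is only ever 1/2, 2/3 or 1, so the count is 16 at each cut-off shown.

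| Predictable with at least | Fixed 4 | 4 or 6 | 2, 4 or 6 |
|---|---|---|---|
| 90% | 16 | about 4 | about 3 |
| 80% | 16 | about 13 | about 24 |
| 75% | 16 | about 23 | about 28 |

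**Why the sizes must stay undisclosed.** A block of 6 has on average 1.5 certain assignments if its size is known. If the realised sizes were known, 4 and 6 would still leave (1.333 + 1.5)/10 = 28% certain.

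**Cost.** At 48 patients the last block may be incomplete. The exact probability of a 25/23 split with sizes 4 or 6 is 0.227, and no larger imbalance can occur. For power, the noncentrality is (14/16)/√(1/n₁ + 1/n₂): 3.031 at 24/24 and 3.028 at 25/23, on 46 degrees of freedom. Power is 84.3% and 84.2%.

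**The case against.** The strongest objection is that the gain depends on counting only certain assignments. A recruiter does not need certainty to lean one way on eligibility, and best-guess accuracy hardly moves. That stands. At 80% the fall is modest, and at 75% the proposed scheme makes more assignments predictable. It also rules out sizes 2, 4 and 6 as an alternative, because they raise the count at 80% from 16 to about 24.

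The second objection is that exposure is not established. The SAP gives no recruitment rate and no interval from surgery to randomization, and it does not say whether the person screening knows every earlier allocation. Open-label delivery makes such knowledge plausible; it does not confirm it. That also stands. Patients approached on the day of surgery may rarely overlap, while those informed at diagnosis may wait longer, so the number pending cannot be settled from the text.

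Third, fixed blocks of 4 guarantee 24/24, which matches the target. That is true, but the most that is lost is one patient moved between arms.

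Two stronger readings are tempting. A reader might infer that concealment is absent because list custody is not described. A short SAP may leave that to other documents, so its silence is missing detail and not a demonstrated flaw. A reader might also infer that any random variation in block size brings the certain share down to about 5%. It does not: the share was about 2% to 13% across the schemes tried, for example 10.8% with sizes 2 and 4.

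**Conclusion.** The point holds as a low-cost improvement to consider; the plan contains no error here. Under the least favourable conditions (block size known, all past allocations visible, nobody pending), a third of assignments, 16 of 48, are certain in advance. The figure falls to 4 with one patient always pending and to 0 with two pending or past allocations hidden. A reader might infer that a third of this trial's assignments are in fact foreseeable, or that its comparison is biased. The documents support neither, because they do not say which condition applies.

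Undisclosed blocks of 4 or 6 give real protection against near-certain prediction when nobody is pending, a smaller gain with one pending, and none with two pending. They do not protect against informed guessing. The results assume 1:1 allocation on one unstratified list, equally likely sizes, and a recruiter who does not learn the realised sizes.

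**What to change.** In Study design, Participants, replace the fixed block of 4 with computer-generated permuted blocks whose size is drawn at random as 4 or 6 with equal probability, and state that the sizes are not disclosed to those who recruit. The sizes themselves are best kept in a restricted document. If randomization has begun, apply this only to patients not yet assigned. Do not use sizes 2, 4 and 6.

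The cost is a regenerated list, a short change of text, a probability of about 23% of finishing 25/23 instead of 24/24, and about 0.1 percentage point of power in that event.

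### Must the SAP fix the outcome, predictors and change interval of the multiple regression that follows the correlation matrix?

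*Combined protocol and SAP*

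**What the plan says.** The regression has one sentence, in Analysis, Secondary outcome: "In addition, a correlation matrix for the changes in secondary and primary outcome will be performed, followed by a multiple regression". The next sentence adds a separate comparison: "ATRA will be compared with MRI and correlated".

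The Table of the analysis ticks the correlation and multiple-regression columns for every row except the Likert scale:

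- "MRI Tendon length CSA tendon CSA muscle Free fat fraction": 4 variables, 4 timepoints.
- "ULTRASOUND Fascicle length Pennation angle Thickness muscle Doppler tendon Thickness tendon": 5 variables, 4 timepoints.
- "HEELRISE Work Height Repetitions": 3 variables, 2 timepoints.
- ATRA, ATRS and PAS: 1 variable each, 2 timepoints.
- "MUSCLE STRENGTH": 1 variable, 1 timepoint.

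Under Per protocol (PP) there is a complete-case rule: "Participants with missing data on any of the variables in the model will be excluded from the specific analysis at the specific timepoint". The Sample size calculation requires 21 patients, read here as per arm, and recruits 24 per arm.

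**The concern.** A reader cannot tell from the SAP which model will be fitted. It could hold every ticked variable, those that stand out in the matrix, one test's measures at a time, or a few chosen measures. Each imaging variable with four timepoints offers several possible changes, whereas heel-rise height offers one. Work and repetitions come from the same test as height, so they could appear to explain it. Strength has a single timepoint, so it has no change over time.

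At stake is the interpretation of mechanism. With many candidates and few patients, some predictor may well look significant by chance, and an unadjusted R-squared near one third could be taken as an explanation of the heel-rise deficit when nothing is there.

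**Working it through.** **1. The plan's own figure.** Inputs from the Sample size calculation: means 76 and 90, SD 16, power 80%. Alpha is not stated; two-sided 0.05 is assumed. n per arm = 2 × (1.96 + 0.842)² × 16² / 14² = 2 × 7.85 × 256 / 196 = 20.5, so 21, as stated. Recruiting 24 corresponds to 12.5% dropout: 21 / 0.875 = 24. The totals are 42 and 48. The plan gives no figure for the regression.

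**2. Candidates.** From the table: 4 + 5 + 3 + 1 + 1 + 1 + 1 = 16, or 15 if heel-rise height is the dependent variable. The Secondary outcomes list gives 10: work, ATRS, fascicle length, pennation angle, tendon area, muscle area, strength, PAS, tendon length and ATRA. Leaving out work and repetitions (same test as height) and strength (no change over time) gives 15 − 3 = 12 from the table and 10 − 2 = 8 from the list. Counting gastrocnemius and soleus separately would raise all of these.

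**3. Simple chance arithmetic.** For k independent null tests at 0.05, P(at least one) = 1 − 0.95^k: 54% for k = 15, 46% for 12, 40% for 10, 34% for 8 and 14% for 3.

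**4. Null simulation.** Chance (%) of at least one predictor with p<0.05 in the final model, normal data, n = 42 / n = 48. The selection rules are assumptions.

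| Rule | 15 candidates | 10 candidates | 3 pre-named |
|---|---|---|---|
| Independent, all entered | 44.9 / 47.0 | 35.9 / 36.6 | 13.8 / 13.3 |
| Independent, screened p<0.05 | 50.6 / 51.5 | 38.8 / 39.1 | – |
| All correlated 0.5, all entered | 44.8 / 45.1 | 34.7 / 36.2 | 12.7 / 13.3 |
| All correlated 0.5, screened p<0.05 | 24.1 / 22.4 | 18.3 / 19.6 | – |
| All correlated 0.5, screened p<0.10 | 14.0 / 12.5 | 12.5 / 12.8 | – |
| All correlated 0.5, backward elimination | 62.3 / 62.4 | 44.4 / 45.9 | – |

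The answer therefore runs from about 12% to 62% depending on a rule and a correlation that the documents do not give.

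**5. R-squared.** Expected null R-squared = k / (n − 1). For k = 15 it is 15/41 = 0.37 and 15/47 = 0.32; for k = 10, 0.24 and 0.21; for k = 3, 0.07 and 0.06. Adjusted R-squared = 1 − (1 − R²)(n − 1)/(n − k − 1). With k = 15 and n = 42 this is 1 − (26/41)(41/26) = 0. In simulation its mean lay within 0.002 of zero and the overall F-test rejected in 4.5–5.6% of runs. Both results hold only when predictors are not chosen from the data.

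**6. Interval.** Four timepoints give C(4,2) = 6 changes; two give 1. If one predictor's interval were picked from six after seeing the results, the false-positive chance would be 19–21% instead of 5%. But heel-rise has only one change, which suggests a matching interval for the imaging measures, and nothing in the SAP suggests picking afterwards.

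**7. Missing data.** If each of seven tests were missing in 5% independently (assumed; range 2–10%), 48 × 0.95⁷ = 33.5 patients would be complete (41.7 to 23.0). If missingness were by visit, with all tests lost together at 5%, 48 × 0.95 = 45.6 would remain. The documents do not say which is nearer.

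**The case for a change.** The strongest case for a change is that the Background ties the project to tendon elongation: "It has been suggested that preventing tendon elongation during rehabilitation improves the clinical outcome, which is the very aim of this project". The regression is where structural change would be linked to function, so it may be read as evidence of mechanism. Naming the model beforehand would cost a few sentences, and naming it afterwards cannot undo selection. The protection from the F-test also fails under selection: if the three variables most correlated with the outcome, out of 15, were put into a model, the overall test would be significant in about 53–54% of null runs. Fitting one model per test does not escape either, with 47–48% across six models.

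What stands is that the specification is thin and that, if the variables were selected from the matrix, p-values and R-squared should not be taken at face value.

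What does not stand is the step to a required change. The SAP states no selection rule, and the higher figures come from supplying one. The 15-candidate case treats work and repetitions as unrelated to height, which a sensible analyst would not do. Most of the contrast between 36–52% and 13–14% is the arithmetic of many unadjusted tests against three, and it is not peculiar to this analysis: the 13 variables ticked for mixed models give 1 − 0.95^13 = 49% on the same independence arithmetic. A short list would lower the count of chance findings but give up breadth in an exploratory analysis, and the choice of predictors would remain with the sponsor.

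**Conclusion.** No change to the plan follows. This is missing detail in a supplementary secondary analysis, of a kind that analysts fill sensibly: heel-rise height as the outcome, a limited set of measures from other tests, matched intervals, adjusted R-squared, and results described as exploratory. The strength tick needs no more than the understanding that a single-visit value or side difference is used, since the column headings refer to correlation and regression rather than to change.

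If many variables were entered, or screened at p<0.05 or p<0.10, the chance of at least one false predictor would be roughly 12–52%, or up to 62% with backward elimination, against 13–14% for three named beforehand. These figures assume alpha 0.05, normal null data, 42 to 48 complete patients, and either independent candidates or a common correlation of 0.5. The selection rules and the correlations are not in the documents. The primary t-test at one year, the mixed models and the sample size are unaffected whatever form the regression takes.
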